7.12. ADDITIONAL SUPPORTING ANALYSES

7.12.1.1. Supportive analysis to further explore clinical significance

Although the structure and methodology for data collection of the MDS-NMS allows for interpretation of the statistically significant changes to be interpreted as inherently clinically meaningful, the scale is relatively new and not well known. As such, to support future clinical adoption by referring physicians, a supplementary analysis is planned as part of the procedures specified in the Statistical Analysis Plan for SNS-PD-002 to establish the MCID for the MDS-NMS. The MCID value identified in the analysis for SNS-PD-002 will define the MCID for analysis in these supporting analyses.

To support the clinical significance of the primary endpoint, the responder rate (i.e., percentage that demonstrate change scores during the first treatment period of the OLE \geq the MCID) in the passive-active treatment group will be reported. Additionally, a McNemar's test will be employed to determine if the responder rate is statistically significantly greater after 12 weeks of tvCVS treatment during the OLE than was the responder rate for this group after 12 weeks of passive treatment during the RCT. The required percentage of participants during the OLE tvCVS that demonstrate a change exceeding the MCID to be statistically significant will be a function of the percentage of participants in the passive-active treatment group that demonstrate a change exceeding the MCID after passive treatment during the RCT. This relationship is depicted in Figure 2. Because the power of this binomial comparison will be reduced under conditions where there is a high responder rate of passive treatment participants during the RCT, if 36% or more of the RCT passive treatment group exceeds the MCID (a condition that would require > 60% responder rate in the active group), the clinical significance for the primary outcome measure will be established by verifying that the

mean difference between responses to the passive treatment RCT and the tvCVS treatment in the OLE exceeds the change equivalent to the MCID.

Effect of Percent in Placebo Group Exceeding MCID

Figure 1: Effect of Percent in Passive (i.e., aka placebo or inactive) Group Exceeding MCID.

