Further, Norman et. al., 2003 (Norman, Sloan et al. 2003) suggested that the MCID be defined as 50% of the standard deviation. Using the standard deviation of 65.87, the MDS-NMS MCID would be 32.9 points. As noted above, however, the proposed study requires subjects to have an MDS-UPDRS Part I score of at least 9 at the study screen. Therefore, utilizing the standard deviation of 70.8 points (Martinez-Martin, *unpublished*), the MDS-NMS MCID would be 35.4 points². As such, the estimated MCID range for improvement in the MDS-NMS for this Statistical Analysis Plan is -32.7 to -35.4 points. While these values provide estimates for sample size calculations, the MCID for the MDS-NMS from data collected within this study using methodology described in section 7.6.1.3.

Notably, the sample size (184 to randomize), derived from the MDS-UPDRS Part I also achieves 85.7% power to detect the estimated MCID minimum of -32.7 and 92.8% power to detect the estimated MCID maximum of -35 points in the MDS-NMS.

Competitive enrollment will be used. Participants will continue to be enrolled until at least 184 are randomized in the RCT, and if there are additional participant withdrawals, they will not be replaced. Any participant who had entered the baseline period but had not yet randomized when the competitive enrollment target is achieved may be withdrawn from the study prior to randomization, and as a result, will not be included in any of the analyses. Data from all randomized study participants will be evaluated for analyses of safety and efficacy. The protocol has planned for up to 290 study participants to be screened. The sample size of 184 to randomize allows for attrition of 10% in the RCT as well as attrition of 10% in the first treatment period of the OLE while still maintaining adequate power to evaluate the primary endpoints of those studies.

[figure not shown]

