7.7. EFFICACY ANALYSIS

Efficacy will be determined using (Zeger and Liang 1992, Zorn 2001) a linear regression utilizing a mixed effects (i.e., mixed model repeated measures [MMRM]). This approach allows for repeated measurements on a subject (i.e., all time points during the study) and unequally spaced as well as missing data (dropouts or intermittent), allows for the inclusion of continuous or categorical covariates, allows for a flexible specification of the covariance structure. This modeling technique has been shown to produce unbiased estimates in the case of data missing at random. Additionally, the MMRM estimation is robust to departures from normality. (Rubin 1987)

The following MMRM model (Zeger and Liang 1992, Zorn 2001) will be analyzed to determine significance for the primary endpoint:

$$\begin{split} Y_{ij} &\sim N(0, \sigma^2) \\ Y_{ij} &= \beta_0 + \beta_1 * ARM_i + \beta_2 * VISIT_{ij} + \beta_3 * ARM_i * VISIT_{ij} + \beta_4 * SITE_i \\ & \text{where:} \end{split}$$

 $Y_{ij} = (MDS_NMS \text{ total score for participant i at time } j) - (MDS_NMS \text{ total score for})$

participant i at baseline),

 $ARM_i = 1$ if participant i is in the treatment arm

= 0 if participant i is in the passive arm,

 $VISIT_{ij}$ = an ordinal variable representing the visit for j^{th} measurement for

participant i

SITE_i is a nominal variable indicating the site for participant i,

An unstructured covariance structure will be utilized for the R matrix. The Kenward-Roger approximation will be used to estimate the denominator degrees of freedom. The difference between active and passive treatment at each visit will be estimated based on the Least Squares Mean (LSMean) difference between the treatment groups at the visit from the MMRM with the associated 90% confidence interval (CI) and 1-sided P-value. Additionally, the p-value for the site effect will be presented. If the unstructured covariance matrix results in convergence issue, the heterogeneous Toeplitz covariance structure followed by the heterogeneous first-order autoregressive (AR(1)) structure will be used. In these cases, sandwich estimators will be obtained from the model fitting procedure to ensure unbiased estimation of the treatment effect.

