7.7.1.2. Clinical Significance

Clinical significance is determined by how a treatment affects the extent to which a participant is currently living independent of help from others OR that there is a real genuine, palpable, and noticeable effect on daily life or how a patient feels, functions, or survives. Importantly, as the scores from the MDS-NMS are derived from the product of the symptom frequency (how often the participant has experienced a given non-motor symptom since the last evaluation with higher scores indicating more frequent experience) and the symptom severity (impact of that symptom on how the participant has felt and functioned with higher scores indicating greater distress or disturbance to patient or caregiver), reductions in MDS-NMS total scores are inherently clinically meaningful in that they represent how the participant is feeling and functioning. Given the inherent clinical meaningfulness of the MDS-NMS total scores, the primary endpoint will be considered clinically meaningful, and therefore, successful, if there is a statistically significant reduction in MDS-NMS total scores in the active tvCVS group relative to the passive treatment group after 12 weeks of twice-daily treatment.

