Once the MCID is determined, it can be used to calculate the percentage of cases that exceed that value for each of the two treatment arms (i.e., responder rates). To further support clinical adoption, a supporting Fisher's exact test analysis will be employed to determine if the responder rate for active treatment participants is statistically significantly greater than the response rate for passive treatment participants. For statistical significance, the required percentage of participants in the intervention group that demonstrate a change exceeding the MCID will be a function of the percentage of participants in the passive treatment group that demonstrate a change exceeding the MCID. This relationship is depicted in Figure 3. Because the power of this binomial comparison will be reduced under conditions where there is a high rate of passive treatment participants that exceed the MCID, if 36% or more of the passive treatment arm exceeds the MCID (a condition that would require > 60% responder rate in the active arm), clinical significance for the primary outcome measure will instead be further supported by verifying that the mean/median difference between the two treatment arms exceeds the change equivalent to the MCID.

[figure not shown]

Figure 3: Effect of Percent in Passive Group Exceeding MCID on the Required Percent of Active Group Needing to Exceed MCID to demonstrate statistical significance using binomial comparison.

Additional analyses of the primary endpoint measure to support clinical adoption will include the following:

• The percent change of scores (normalized to the average baseline)

The percent change of scores is calculated as the mean change score divided by the mean baseline value multiplied by 100.

• The percentage of participants who improved by 1 MCID or more (i.e., change from baseline in MDS-NMS Total Score at Day 113 ≥ MCID calculated on an individual level). Participants who do not meet this criterion are non-responders.

The proportion of participants whose change from baseline to Day 113 in NMS-MDS total score met or exceeded the MCID will be summarized by treatment group.

• Effect Sizes

Effect size will be calculated in two ways:

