- a. Cohen's w will be calculated for the 2x2 table of responders/non-responders and treatment group. Cohen's w is calculated as the square root of the chisquare test statistic divided by the total number of participants. Responders are defined as those participants with change from baseline in MDS-NMS Total Score at Day 113 ≥1 MCID. Non-responders are those who did not respond (includes missing data as non-responders).
- b. Cohen's D will be derived as the ratio of the estimated difference in the change from baseline MDS-NMS to the population standard deviation at each visit estimated from the model (the square root of the diagonal elements of the estimated covariance matrix).
- The number needed to treat to obtain 1 patient with improvement of 1 MCID or more

The number needed to treat is calculated as 1/the absolute difference between treatment groups in the proportion of non-responders (i.e., change from baseline in MDS-NMS Total Score at Day 113 < MCID or missing).

• Reliable Change Index

Reliable Change Index is defined per participant as the difference of the pre and post treatment scores divided by the standard error of the measurement. The standard error of the measurement is calculated as the square root of two times the standard error of the mean difference between pre and post treatment scores, squared ($\sqrt{2(\text{SEM}^2)}$). This value is compared to the cutoff score assuming a normal distribution and 95% confidence level. The proportion of values above (RC+), below (RC-), and at (RCo) the cutoff value will be presented. This value will be calculated for the change from baseline in MDS-NMS Total scores at Day 113.

• Cumulative Distribution Plot

A plot of the cumulative distribution of the change from baseline in MDS-NMS Total scores at Day 113 will be prepared.

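### The MDS-NMS responder inequality has the wrong sign for a score on which improvement is a reduction: a minor wording correction to supportive analyses in the RCT and OLE SAPs

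*SAP*

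**What the plan says.** **Change score and direction.** The model in RCT SAP 7.7 defines the outcome as the score at a visit minus the baseline score. Section 7.7.1.2 says "reductions in MDS-NMS total scores are inherently clinically meaningful". Improvement is therefore a negative change.

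**Responder rule.** Section 7.7.1.3 gives the rule in three places:
- The responder percentage is introduced as "The percentage of participants who improved by 1 MCID or more" and then glossed as "change from baseline in MDS-NMS Total Score at Day 113 ≥ MCID calculated on an individual level".
- For Cohen's w: "Responders are defined as those participants with change from baseline in MDS-NMS Total Score at Day 113 ≥1 MCID". Missing data count as non-response.
- For the NNT, the title of the item speaks of improvement by at least one MCID, but a non-responder is defined by "change from baseline in MDS-NMS Total Score at Day 113 < MCID or missing".

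The Fisher test in the same section compares the percentages of cases exceeding the MCID and asks whether the active rate is greater.

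**OLE.** OLE SAP 7.12.1.1 describes the responder rate as the "percentage that demonstrate change scores during the first treatment period of the OLE" at or above the MCID. It compares this with the passive RCT period by McNemar's test.

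**Sign of the MCID.** RCT SAP 4 says "the estimated MCID range for improvement in the MDS-NMS for this Statistical Analysis Plan is -32.7 to -35.4 points" but also gives 32.7 and 35.1 without a sign. The distribution-based fallback in 7.7.1.3 (0.3 times the baseline SD) is positive by construction. The sign of the ROC-derived value is not stated.

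**The concern.** A negative change cannot be tested for improvement with a greater-than-or-equal inequality. With a negative MCID, the rule calls a responder anyone who did not improve by more than the MCID, including those who got worse. With a positive MCID, it calls a responder only someone who worsened by at least that much. Because the sign of the MCID is not fixed, two programmers could build different flags and both be wrong.

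The flag feeds the responder percentages, the Fisher test, Cohen's w, the NNT, the 36% switch to a mean or median comparison and, in the OLE, the responder rate and McNemar test. These outputs are meant to support clinical adoption and the clinical reading of the primary result, so a reversed table would be visible and damaging even though it decides nothing confirmatory.

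**Working it through.** **1. The plan's own figures.** RCT SAP 4 sizes the trial at 83 completers per arm for 2.64 points with SD 5.32 and two-sided alpha 0.05. Normal approximation: 2.64 / (5.32 × √(2/83)) = 3.197; 3.197 − 1.960 = 1.237; Φ(1.237) = 0.892, matching the stated 89.2%. The MCID estimates also reproduce: 2.64/5.32 = 0.496; 0.496 × 65.87 = 32.7; 0.496 × 70.8 = 35.1; 0.5 × 70.8 = 35.4. The documents give no expected responder rate, NNT or w, so no stated figure rests on the disputed rule.

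**2. Inputs for the responder check.** From the SAP: SD 70.8 and |MCID| 35.4. The true active-minus-passive effect is set at −35, the value at the upper end of the SAP's power statement. Assumed, because the documents do not say: individual changes are normal, the quoted cross-sectional SD serves as the SD of change, passive mean change is 0, and no data are missing.

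**3. Responder proportions.**
- Intended rule, change ≤ −35.4: passive Φ(−35.4/70.8) = Φ(−0.500) = 0.309; active Φ((−35.4 + 35)/70.8) = Φ(−0.006) = 0.498.
- Literal rule, MCID = −35.4: the complements, passive 0.691 and active 0.502.
- Literal rule, MCID = +35.4: passive 1 − Φ(0.500) = 0.309; active 1 − Φ(70.4/70.8) = 1 − Φ(0.994) = 0.160.

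**4. Derived measures.** NNT = 1/|difference|. With equal arms, w = |difference| / (2√(p̄(1 − p̄))), where p̄ is the mean of the two rates.

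| Rule | Active | Passive | Difference (points) | NNT | w |
|---|---|---|---|---|---|
| Intended | 49.8% | 30.9% | +18.9 | 5.3 | 0.193 |
| Literal, MCID −35.4 | 50.2% | 69.1% | −18.9 | 5.3 | 0.193 |
| Literal, MCID +35.4 | 16.0% | 30.9% | −14.9 | 6.7 | 0.175 |

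**5. Range.** SD 65.87 or 70.8; |MCID| 0.3 SD, 32.7 or 35.4; passive mean 0 or −15; missing 0 or 10% in both arms:
- Intended: +17.0 to +21.0 points; NNT 4.8 to 5.9; w 0.174 to 0.210.
- Literal, negative MCID: −17.0 to −21.0 points; NNT 4.8 to 5.9; w 0.171 to 0.210.
- Literal, positive MCID: −11.2 to −17.9 points; NNT 5.6 to 8.9; w 0.153 to 0.197.

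**6. The 36% switch.** In the base case the passive rate is 30.9% under the intended rule, so the switch stays off. It is 69.1% under the literal negative rule, so the switch fires. The positive reading can err the other way: with passive mean −15, the intended passive rate is 38.7% (switch on) but the literal rate is 23.8% (switch off).

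**7. Unequal missingness.** Take |MCID| 35.1 and active mean −35.1, so intended rates among observed participants are 0.500 and 0.310. Missing counts as non-response throughout.
- 15% active and 5% passive missing. Intended: 0.85 × 0.500 − 0.95 × 0.310 = 0.1305, NNT 7.7. Literal negative: 0.85 × 0.500 − 0.95 × 0.690 = −0.2305, NNT 4.3.
- Missingness swapped. Intended: 0.95 × 0.500 − 0.85 × 0.310 = 0.2115, NNT 4.7. Literal negative: 0.95 × 0.500 − 0.85 × 0.690 = −0.1115, NNT 9.0.

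The absolute value in the NNT would hide a reversed table while reporting a wrong number.

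**The case against.** The intended direction is on the page. The inequality for the responder percentage is a gloss on a phrase about participants who improved, the NNT item is titled in terms of improvement, and the two-by-two table behind the MCID cut-off classes participants as improving or not. For the secondary endpoints (7.7.2.1, 7.7.2.3 and 7.7.2.4) the SAP lets a change meet or exceed a negative MCID, plainly meaning magnitude, so the inequality may be shorthand for that. The signed range in section 4 was given for sample size, whereas the responder rule uses the in-study MCID. Section 7.1 also promises formal verification and review by the lead statistician, which should catch a reversed table.

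Most of this stands. It shows what was meant and lowers the chance that the error reaches a report. It does not make the rule correct. The operative inequality contradicts the words beside it, and the Cohen's w definition and OLE 7.12.1.1 carry no improvement wording in the rule itself. Nor does the rule work with either sign of the MCID, so the purpose of the section 4 range does not matter.

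A reader might go further and infer that the plan intends to count worsening as response, or that the NNT and effect sizes would make an effective device look harmful. The documents support neither. Improvement is named twice beside the rule. The NNT uses an absolute difference and w is the root of a chi-square, so neither can point towards harm. Cohen's D comes from the model and does not use the responder flag.

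**Conclusion.** The stated inequality is wrong for either sign of the MCID and should be corrected. Under literal coding the responder rates and the directional Fisher comparison reverse: an intended advantage of 17 to 21 points becomes a deficit of 17 to 21 points (negative MCID) or 11 to 18 points (positive MCID). The 36% switch can be set wrongly, and the OLE responder rate and McNemar test share the exposure. The NNT is unchanged with a negative MCID if missingness is nil or equal between arms; w is unchanged if nothing is missing and moves only slightly if missingness is equal. Both are distorted with a positive MCID or unequal missingness.

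These sizes rest on the assumptions in the working; the reversal itself follows from the sign convention whenever the active arm truly improves more.

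It would be tempting to call this a must-fix that threatens the trial's conclusion. The documents do not bear that out. Primary success in 7.7.1.2 depends on a significant reduction in mean score, and no responder analysis is in the testing hierarchy of 7.7.2. This is a minor correction to supportive analyses.

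**What to change.** In RCT SAP 7.7.1.3, define improvement as baseline minus end-of-treatment (Day 113) score. Define a responder as improvement ≥ |MCID|, equivalently change from baseline ≤ −|MCID|, and a non-responder as improvement < |MCID| or missing. State one sign convention for the MDS-NMS MCID and keep to it in section 4, the ROC derivation and the 0.3 SD fallback. Use the same definition for the responder percentages, the Fisher test, the 36% switch, Cohen's w and the NNT.

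In OLE SAP 7.12.1.1, repeat the definition for each period, using the OLE baseline and EOT1 (Day 197) for the OLE period and the RCT baseline and Day 113 for the passive period.

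The cost is a few lines of SAP text before the flags are programmed. No new data are needed, and the sample size, the primary test and the hierarchy do not change.

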4. SAMPLE SIZE DETERMINATION

The sample size for this study was set to achieve ~ 90% power to detect a minimal clinically important difference (MCID) of -2.64 points in the MDS-UPDRS: Part I (Horvath, Aschermann et al. 2017) for both the RCT and the first treatment period during the OLE. This estimated group sample sizes of 83 and 83 (166 total) to complete the RCT (assuming 10% attrition) achieves 89.2% power to detect a difference of 2.64 points in the MDS-UPDRS Part I total score for the null hypothesis that both group average change scores are equal and the alternative hypothesis that the average change score of the active treatment group represents greater symptomatic improvement than that of the passive treatment group given an estimated within group standard deviation of 5.32 points and a 2-sided significance level (alpha) of 0.05.

This sample size also achieves > 90% power to evaluate the primary endpoint of the STEM-PD OLE (see the STEM-PD OLE SAP for additional details).

Note that the primary outcome measure for the STEM-PD RCT is the MDS-NMS, not the MDS-UPDRS: Part I. However, the two scales are highly correlated (correlation coefficients = 0.75-0.85) (Chaudhuri, Schrag et al. 2019, van Wamelen, Martinez-Martin et al. 2021), and the MDS-UPDRS Part I has a pre-established MCID whereas the MDS-NMS does not. Given the high correlation reported for these two outcome measures in previous studies, an analysis was performed to estimate the MCID for the MDS-NMS. The MCID for the MDS-UPDRS: Part I is

2.64 points (Horvath, Aschermann et al. 2017). Since the estimated standard deviation of the MDS-UPDRS Part I for this study is 5.32 points, the MCID represents 49.6% of the standard deviation.

The standard deviation of the MDS-NMS scale has been reported as 65.87 points (Chaudhuri 2020). Using the same proportion of the standard deviation, the estimated MCID for the MDS-NMS scale for this study would be 32.7 points. Additionally, in an unpublished study analysis of participants from the original validation study, Martinez-Martin determined that among a cohort with MDS-UPDRS Part I scores greater than 10, which approximates the inclusion criterion for this study, the standard deviation of the MDS-NMS was 70.8 points. Utilizing a definition of 49.6% of the standard deviation, based upon the Martinez-Martin study, the MCID for the MDS-NMS scale would be 35.1 points.

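### The Reliable Change Index divisor is named as a measurement error but calculated from a group-mean standard error, so as written its 95% cut-off would class most participants as changed under noise alone

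*SAP*

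**What the plan says.** The RCT SAP (Appendix 1 to the OLE SAP), section 7.7.1.3, lists further analyses of the MDS-NMS total score meant to support clinical adoption. One is the Reliable Change Index for the change from baseline to day 113:

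- Definition: "Reliable Change Index is defined per participant as the difference of the pre and post treatment scores divided by the standard error of the measurement".
- Divisor: "The standard error of the measurement is calculated as the square root of two times the standard error of the mean difference", followed by the formula sqrt(2(SEM^2)). The full phrase for the quantity inside the root is "the standard error of the mean difference between pre and post treatment scores".
- Cut-off: "This value is compared to the cutoff score assuming a normal distribution and 95% confidence level".
- Output: "The proportion of values above (RC+), below (RC-), and at (RCo) the cutoff value will be presented".

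No other definition of the divisor appears in either document, and neither gives a reliability coefficient for the MDS-NMS.

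**The concern.** A reliable change index asks whether one person's change exceeds what that person's measurement error could produce. Its divisor therefore has to describe error in an individual score. The standard error of a mean difference describes uncertainty in a group average. If it is used for individuals, the same change in the same participant becomes more reliable merely because more people were enrolled, and the stated 95% level cannot hold.

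The section contradicts itself: the quantity it names is suitable, but the calculation it gives is not. A programmer following the calculation would produce RC+ and RC- percentages that look like shares of participants with real individual change, when a large part could be ordinary fluctuation. Because no reliability source is named, correcting the formula after unblinding would also leave a choice open at the wrong time.

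**Working it through.** **Inputs**

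- Numerator: the individual difference D, from section 7.7.1.3.
- Divisor as written: sqrt(2) x SD_diff / sqrt(n), where SD_diff is the SD of the pre-post differences.
- Cut-off: 1.96. Two-sided is inferred from the existence of both RC+ and RC-.
- n: section 4 of the RCT SAP says "This estimated group sample sizes of 83 and 83 (166 total) to complete the RCT (assuming 10% attrition) achieves 89.2% power". Section 7.7.1.3 does not say whether the standard error is taken per arm or pooled, so n = 83 and n = 166 are both assumptions. As a check on the planning figures, a difference of 2.64 with SD 5.32, 83 per arm and two-sided alpha 0.05 gives power 0.892 by the normal approximation, which matches the stated 89.2%.

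**Step 1: the plan's own figure.** A 95% level implies that about 5% of participants are classed as changed when nothing has changed. Under no true change, D is taken as normal with mean 0 and SD equal to SD_diff. As written, the index exceeds 1.96 in size when |D| > 1.96 x sqrt(2/n) x SD_diff. Hence

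P(classed as changed) = 2 x (1 - Phi(1.96 x sqrt(2/n))).

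SD_diff cancels, so no outside figure is needed.

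| n | Cut-off in SDs of change | Classed as changed | Each direction |
|---|---|---|---|
| 83 (per arm) | 1.96 x sqrt(2/83) = 0.304 | 76.1% | 38.0% |
| 166 (pooled) | 1.96 x sqrt(2/166) = 0.215 | 83.0% | 41.5% |

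The nominal values are 1.96 SD, 5% and 2.5%, so the stated level is not reproduced. With all 184 randomized participants the share is 83.8%. It exceeds 50% from n = 17 upwards.

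**Step 2: simulation.** In 5,000 noise-only trials per setting (SD 70.8, reliability 0.9), the share was 76.3% at n = 83 and 83.1% at n = 166 with a single baseline. With the two-visit mean baseline it was 76.2% and 83.0%.

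**Step 3: alternative readings.** Dropping the sqrt(2) gives 83.0% at n = 83. A one-sided cut-off of 1.645 gives 39.9% in each tail at n = 83. Reading the phrase as the SD of the differences removes the inflation, but it contradicts the wording and gives 0.56%, which is not 5% either.

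**Step 4: scale in points.** Section 4 states "The standard deviation of the MDS-NMS scale has been reported as 65.87 points" and gives 70.8 for a cohort closer to this trial's entry criterion. Reliability r is not in the documents and is assumed here. For SD 70.8, r = 0.9 and a single baseline:

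- Standard error of measurement = 70.8 x sqrt(0.1) = 22.4.
- SD_diff = 22.4 x sqrt(2) = 31.7.
- Usual cut-off = 1.96 x 31.7 = 62.1 points.
- Cut-off as written = 0.304 x 31.7 = 9.6 points (n = 83) or 0.215 x 31.7 = 6.8 points (n = 166).

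Over assumed r from 0.70 to 0.95 and SD from 65.87 to 70.8, the usual cut-off runs from about 41 to 108 points. The one written runs from about 6 to 17 (n = 83) or 4.5 to 12 (n = 166).

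**Step 5: the replacement.** With a divisor that does not shrink with n, the simulated noise-only share is 5.0% for a single baseline with sqrt(2). For the two-visit mean baseline the error variance of the change is SEM^2 + SEM^2/2 = 1.5 x SEM^2. The factor sqrt(1.5) then gives 4.9% to 5.0%, whereas sqrt(2) gives about 2.4%.

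**The case against.** The best defence is that this is a slip of terminology. The SAP names the right quantity and writes the usual sqrt(2(SEM^2)) form; a single phrase confuses two meanings of SEM. A statistician who knows the index might program it correctly regardless. That is plausible, but the conflicting phrase is the only calculation given, so the point stands on the text and the result is conditional on following it literally.

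Three further points limit the consequence, and all of them stand:

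- The index is descriptive. No test is attached to the RC proportions. Individual benefit is also addressed in the same section by MCID responder rates with Fisher's exact test, the number needed to treat and a cumulative distribution plot, none of which uses this formula.
- The inflation is symmetric under noise. At n = 83 about 38% would appear reliably worsened as well as 38% improved, which would be conspicuous. A reader might infer that the error favours the device; with no effect and equal arms it does not.
- The 76% and 83% assume no true change and normal differences. A reader might infer that most RC+ cases actually reported would be noise. If there is real change, the mix is unknown, so the documents do not support that.

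A reader might also infer that the trial's claim of clinical significance is undermined. It is not: section 7.7.1.2 rests that claim on a statistically significant MDS-NMS difference, and the hierarchy in section 7.7.2 does not include this index.

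**Conclusion.** The divisor is wrong as written. Followed literally, a cut-off labelled 95% would class 76% (n = 83, per arm) or 83% (n = 166, pooled) of participants as changed when none has truly changed. These shares rest on normal differences, a two-sided 1.96 cut-off and the assumed n; they do not depend on any assumed SD or reliability. The cut-offs in points do depend on an assumed reliability.

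The output categories have a related fault: RCo is defined as values at the cut-off, which is practically empty, so participants between the two limits have no proper category.

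The damage is confined to one supportive, descriptive analysis. It should be corrected because its output would be read as the share of individuals with genuine change, but it does not bear on the primary result.

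**What to change.** Rewrite the Reliable Change Index paragraph in RCT SAP 7.7.1.3, before unblinded data are used for it:

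- **Standard error of measurement:** single-visit baseline SD x sqrt(1 - r). Specify single-visit. The SD of the averaged baseline is smaller by a factor sqrt((1 + r)/2) and, with the sqrt(1.5) divisor below, would give noise-only rates of 9.0%, 7.1% and 5.6% for assumed r of 0.5, 0.7 and 0.9.
- **Reliability r:** the correlation of the day 0 and day 29 MDS-NMS totals in this trial, or another source named in advance. If the trial's own correlation is used, note that day 0 is a virtual visit and day 29 is in clinic about four weeks later, so r absorbs any effect of mode and interval.
- **Divisor:** SEM x sqrt(1.5) when baseline is the mean of the two visits, as in section 7.7.1, assuming independent errors of equal variance. Use SEM x sqrt(2) for the day-29-only baseline of section 7.10.5.
- **Categories:** cut-offs of -1.96 and +1.96, with RCo defined as values between them.

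The cost is one rewritten paragraph. Both pre-treatment MDS-NMS assessments are already in the schedule of events, so no new data are needed. The downside for the sponsor is that the RC+ and RC- percentages will fall.

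### The Reliable Change Index is classed around one unstated cutoff, so its middle class is essentially empty and RC- mixes unchanged participants with one tail

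*SAP*

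**What the plan says.** The Reliable Change Index is one of the additional analyses of the primary endpoint listed in RCT SAP section 7.7.1.3, which are there to support clinical adoption. The section gives these elements:

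- **Numerator:** "Reliable Change Index is defined per participant as the difference of the pre and post treatment scores". The order of subtraction is not given.
- **Divisor:** "the square root of two times the standard error of the mean difference between pre and post treatment scores, squared".
- **Cutoff:** "This value is compared to the cutoff score assuming a normal distribution and 95% confidence level". It is in the singular and has no numerical value.
- **Classes:** "The proportion of values above (RC+), below (RC-), and at (RCo) the cutoff value will be presented".
- **Outcome and time:** "This value will be calculated for the change from baseline in MDS-NMS Total scores at Day 113".

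The labels RC+, RC- and RCo are not defined in words. No other section of the RCT SAP supplies a second limit or an interval for RCo, and the main body of the OLE SAP does not mention the index.

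**The concern.** Three labels of the form plus, zero and minus suggest a split into change one way, no reliable change, and change the other way. That split needs two limits. One limit gives only two classes of any size, because the third, being exactly at the limit, holds almost nobody. Everyone whose index falls short of the cutoff then goes into RC-, whether unchanged or changed in the opposite direction.

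Which direction is lost depends on the sign, which the section leaves open. Lower scores are better: "reductions in MDS-NMS total scores are inherently clinically meaningful in that they represent how the participant is feeling and functioning" (section 7.7.1.2). If the index is pre minus post, RC- mixes unchanged participants with those who worsened. The model in section 7.7 defines change as the later score minus baseline. With that sign and a positive cutoff, RC- mixes unchanged participants with improvers.

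At stake is a table meant to help prescribers judge individual response, in which the RC- percentage would have no clear meaning.

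**Working it through.** The documents give no index value, cutoff or class proportion, so there is no stated figure to reproduce. The check applies the written rule and the two-limit rule to the same distribution.

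**Inputs**

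- Cutoff c: not in the SAP. Assumed 1.96 (two-sided 95%), with 1.645 as the alternative because the efficacy tests in sections 7.7 and 7.7.1.1 are one-sided at 5%.
- n = 83 completers per arm, 166 in total (section 4).
- SD of the MDS-NMS: "the standard deviation of the MDS-NMS was 70.8 points" (section 4, cohort with higher MDS-UPDRS Part I scores). Used only in step 1.

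**Step 1. Is RCo empty?** I simulated 2,000 samples of 83 participants with whole-number scores (assumed mean 100, SD 70.8, floor at 0, scores drawn independently at each visit, baseline as the mean of two) and the SAP's divisor. Of 2,000 × 83 = 166,000 index values, none equalled 1.96.

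**Step 2. Valid index, no true change.** Take the index as normal with mean 0 and SD 1.

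- As written: RC+ = P(Z > c), RC- = P(Z < c), RCo = 0.
- Two limits: RC+ = P(Z > c), RC- = P(Z < -c), RCo is the remainder.

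| c | Rule | RC+ | RCo | RC- |
|---|---|---|---|---|
| 1.96 | as written | 2.5% | 0% | 97.5% |
| 1.96 | two limits | 2.5% | 95.0% | 2.5% |
| 1.645 | as written | 5% | 0% | 95% |
| 1.645 | two limits | 5% | 90% | 5% |

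The distribution is symmetric about zero, so these figures hold for either sign.

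**Step 3. The SAP's own divisor, no true change.** The standard error of the mean difference is SD_change/√n, so the divisor is √2 × SD_change/√n. An index of c then corresponds to a change of c × √(2/n) in units of SD_change. With n = 83 and c = 1.96 this is 1.96 × √(2/83) = 0.304.

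- As written: RC+ = P(Z > 0.304) = 38.0%, RCo = 0%, RC- = P(Z < 0.304) = 62.0%.
- Two limits: 38.0% / 23.9% / 38.0%.

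The SAP does not say whether the standard error is taken by arm or pooled. At n = 166, RC- is 58.5% as written against 41.5%.

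**Step 4. Why the sign matters.** Take the valid index, c = 1.96, and an assumed mean improvement of one index unit.

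- Pre minus post (mean +1): RC- is 83.2% as written against 0.15% with two limits.
- Post minus baseline (mean -1): by symmetry RC+ is 0.15%, so RC- as written is 100 - 0.15 = 99.85%, against 16.9% with two limits, and that 16.9% are the reliable improvers.

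With the SAP's divisor, pre minus post, n = 83 and an assumed mean improvement of 0.3 SD of the change scores, RC- is 50.2% as written against 27.3%.

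**The case against.** The strongest reply is that this is loose drafting. Plus, zero and minus labels with a normal distribution and 95% confidence point to symmetric limits, and an experienced programmer would code ±1.96. That may well happen, but the text does not say it. Section 7.1 requires formal verification of all analyses, and section 1 says deviations from the plan will be described in the study report. A verifier must either reproduce the literal table or replace it with an unwritten rule.

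A reader might infer that everyone without reliable improvement will be reported as reliably worse, or that an effective device would appear to have worsened 83% of its users. The documents do not support either statement. The SAP never says RC- means worse. It does not fix the sign, and the model in section 7.7 uses the opposite one. It does not state 1.96. The 83% also combines the literal cutoff with a divisor that the SAP does not use.

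Two further points stand. A second limit alone does not make the table valid: step 3 gives 38/24/38 with no true change. And the consequence is limited. This is one descriptive item with no test, alpha or success criterion. A cumulative distribution plot of the same day 113 changes is also planned, so worsening would remain visible there.

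**Conclusion.** The rule is wrong as written. One cutoff cannot produce the three classes: RCo is essentially empty, and RC- pools participants without reliable change with one tail, the identity of which depends on a sign that the SAP leaves open. With no true change, the written rule inflates RC- from 2.5% to 97.5% (c = 1.96) or from 5% to 95% (c = 1.645) for a valid unit-variance index. With the SAP's literal divisor at n = 83 and c = 1.96, it goes from about 38% to 62%.

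These sizes rest on normality and on an assumed cutoff. That RCo means no reliable change is the natural reading of the labels, but it is not a stated definition. The point is minor: it affects one supportive table, and not the primary test, the alpha level or the sample size.

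**What to change.** In RCT SAP section 7.7.1.3:

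- define the index on baseline minus day 113, so that improvement is positive;
- state the cutoff c numerically (1.96 for two-sided 95%);
- set RC+ as index > +c, RC- as index < -c, and RCo as -c to +c inclusive;
- say in words what each label means;
- present the three proportions by treatment arm.

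This takes a sentence or two and needs no new data or analysis.

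The divisor must be corrected in the same edit. It uses the standard error of a group mean, which shrinks as n grows, where the index needs the error of one person's change. That is a separate defect and requires a stated source for the measurement error. Without it, the two-limit table would still not be a valid reliable-change table.
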